2.2 Study variables

2.2.1 Efficacy variables

2.2.1.1 Primary efficacy variable

The primary efficacy variable is:

- Change from Baseline in quantitative myasthenia gravis (QMG) score to Visit 9 (Day 29)

2.2.1.2 Secondary efficacy variables

The secondary efficacy variables are:

- Change from Baseline in MG-Composite score to Visit 9 (Day 29)
- Change from Baseline in myasthenia gravis-Activities of Daily Living (MGADL) score to Visit 9 (Day 29)

2.2.1.3 Other efficacy variables

The other efficacy variables are:

- Value and change from Baseline in QMG at each scheduled assessment during Treatment and Observation Periods
- QMG responder (≥ 3.0 point improvement from Baseline) at each scheduled assessment during Treatment and Observation Periods
- Value and change from Baseline in MG-Composite score at each scheduled assessment during Treatment and Observation Periods
- MG-Composite responder (≥ 3.0 point improvement from Baseline) at each scheduled assessment during Treatment and Observation Periods
- Value and change from Baseline in MGADL at each scheduled assessment during Treatment and Observation Periods
- MGADL responder (≥ 3.0 point improvement from Baseline) at each scheduled assessment during Treatment and Observation Periods
- Myasthenia Gravis Foundation of America (MGFA) classification at each scheduled assessment during Treatment and Observation Periods
- Value and change from Baseline in MG muscle weakness and fatigability at each scheduled assessment during Treatment and Observation Periods
- Value and change from Baseline in fatigue at each scheduled assessment during Treatment and Observation Periods
- Value and change from Baseline in Myasthenia Gravis Impairment Index (MGII) scores at each scheduled assessment during Treatment and Observation Periods
- Value and change from Baseline in MGII ocular sub-scores at each scheduled assessment during Treatment and Observation Periods
- Value and change from Baseline in MGII generalized domain sub-scores at each scheduled assessment during Treatment and Observation Periods
- Change in the percentage of normal fiber pairs in jitter [single fiber electromyography (SFEMG)] studies from Baseline to Visit 9 for the subjects consenting to this measurement at the participating sites
- Change in mean consecutive difference (MCD) of the interpotential interval (IPI) in jitter (SFEMG) studies from Baseline to Visit 9 for the subjects consenting to this measurement at the participating sites
- A reduction in MCD of $\geq 9\mu\text{s}$ in jitter (SFEMG) studies will define clinically meaningful improvement

2.2.2 Other and exploratory variables

2.2.2.1 Safety variables

The safety variables are the following:

- Occurrence of treatment-emergent adverse events (TEAEs)
- Vital sign values and changes from Baseline (systolic and diastolic BP, temperature, pulse rate, respiratory rate, and body weight) at each scheduled assessment during Treatment and Observation Periods
- 12-lead ECG values and change from Baseline at each scheduled assessment during Treatment and Observation Periods
- Laboratory values and changes from Baseline at each scheduled assessment during Treatment and Observation Periods (hematology, clinical chemistry, and urinalysis)
- Change from Baseline in exploratory safety biomarkers (may include but not limited to [REDACTED]) in subjects with severe headache and/or moderate to severe GI disturbance
- TEAEs leading to withdrawal of investigational medicinal product (IMP)

The clinical safety laboratory tests are detailed in [Table 11-1](#).

2.2.2.2 Pharmacokinetic variable

The PK variable is the following:

- Plasma concentration of UCB7665 at each scheduled assessment during Treatment and Observation Periods

2.2.2.3 Pharmacodynamic variables

The PD variables are the following:

- Minimum value and maximum (absolute and percentage) decrease from Baseline in total serum IgG concentration during the study
- Value and change (absolute and percentage) from Baseline in total serum IgG concentrations at each scheduled assessment during Treatment and Observation Periods
- Value and change (absolute and percentage) from Baseline in serum IgG subclass concentrations at each scheduled assessment during Treatment and Observation Periods
- Change in MG-specific autoantibody [REDACTED] levels in serum from Baseline at each scheduled assessment during Treatment and Observation Periods

2.2.2.4 Immunological variables

The other immunological variables are the following:

- Change from Baseline in serum immunoglobulin (Ig) concentrations (total IgA, IgE, and IgM) at each scheduled assessment during Treatment and Observation Periods
- Change from Baseline in serum complement levels (C3 and C4) and plasma complement levels (C3a and C5a) predose at Visit 2 and 4 hours postdose at each scheduled assessment during Treatment and Observation Periods
- [REDACTED] ([REDACTED]) status (negative or confirmed positive) and either change from Baseline in relative mass units at each scheduled assessment during Treatment and Observation Periods or titre for those confirmed positive

- Change from Baseline in serum BAFF levels
- Change from Baseline in cytokines pre- and postdose (postdose - in subjects experiencing infusion reactions) at assessments during Treatment and Observation Periods
- Change from Baseline in [REDACTED] antibodies
- Change from Baseline in exploratory biomarkers relating to mechanism of action, disease activity, treatment response, and clinical outcome

2.3 Study design and conduct

This is a Phase 2a, multicenter, randomized, investigator- and subject-blind, placebo controlled, 2-arm, repeat dose, treatment sequence study evaluating the safety and efficacy of UCB7665 as a chronic-intermittent treatment for subjects with moderate to severe generalized MG.

Approximately 42 randomized subjects will be enrolled at approximately 30 sites from Europe, United States of America (USA), and Canada to achieve the targeted number of 40 evaluable subjects.

The maximum duration of the study per subject is approximately 18 weeks, consisting of a Screening Period (1 to 28 days), Treatment Period (6 weeks), and an Observation Period (8 Weeks).

Screening Period: The purpose of the Screening Period is to evaluate and confirm the subject's eligibility. The Screening Period should not exceed 28 days in total.

Treatment Period: The Treatment Period will consist of Dosing Period 1 followed by Dosing Period 2. Subjects will receive 3 doses of IMP at weekly intervals during each Dosing Period as follows.

- Dosing Period 1 will be 4 weeks, with 2 parallel Treatment Groups (UCB7665 7mg/kg or placebo).
- Dosing Period 2 will be 2 weeks, with 2 parallel Treatment Groups (UCB7665 7mg/kg or UCB7665 4mg/kg).

Prior to receiving an infusion with IMP, subjects will be assessed for efficacy measurements at each visit in the Treatment Period. All safety and efficacy measurements must follow the order specified in the Study Procedures Manual.

Dosing Period 1: Dosing Period 1 will last for approximately 4 weeks (Day 1 to Day 28) and includes Visits 2, 3, 4, 5, 6, 7, and 8. Following completion of the Screening Period, eligible subjects will check-in at the clinic/hospital for the Randomization Visit (Visit 2). Subjects who continue to meet eligibility requirements will be randomized 1:1 to receive 7mg/kg of UCB7665 or placebo, administered by an approximately 30 minute sc infusion at weekly intervals for 3 weeks (Visits 2, 4, and 6) followed by an assessment visit at Week 4 (Visit 8). At Visits 2, 4, and 6 in Dosing Period 1, subjects will be required to remain in the clinic/hospital for at least 4 hours for safety monitoring after the infusion. Subjects may leave the clinic/hospital once the safety monitoring postdose period is over and the investigator or designee has no safety concerns. A follow-up telephone call will be conducted 24 hours postdose to assess the status of the subject (Visits 3, 5, and 7). Subjects will return to the clinic/hospital at Visit 8 for safety and efficacy assessments. The primary efficacy endpoint, change from Baseline in the QMG score, will be

[figure not shown]
assessed at the beginning of Dosing Period 2 at Visit 9 (Day 29) prior to rerandomization . The efficacy assessments that are performed at Visit 9 will therefore occur 2 weeks after the final dose of study drug in Dosing Period 1.

Dosing Period 2: Dosing Period 2 will last for approximately 2 weeks (Day 29 to Day 43) and includes Visit 9, 10, 11, 12, 13, and 14. Subjects will return to the clinic for Visit 9, 11, and 13 for safety and efficacy assessments. At Visit 9, following the administration of safety and efficacy assessments, subjects initially randomized at Baseline to placebo or to 7mg/kg of UCB7665 will be rerandomized 1:1 to receive either 3 doses of 7mg/kg or 3 doses of 4mg/kg administered by a 30 minute sc infusion at weekly intervals (Visit 9, 11, and 13). The interactive response technology (IRT) will stratify the rerandomization based on the treatment received in Dosing Period 1. At each weekly clinic visit in Dosing Period 2 (Visits 9, 11, and 13), subjects will be required to remain in the clinic/hospital for at least 4 hours safety monitoring postdose period as determined. Subjects may leave the clinic/hospital once the safety monitoring postdose period is over and the investigator or designee has no safety concerns. A follow-up telephone call will be conducted 24 hours post dose to assess the status of the subject (Visits 10, 12, and 14).

Observation Period: All subjects must be followed for 8 weeks after the final dose of IMP is administered. Subjects will return to the clinic for Visits 15, 16, and 18 for efficacy and for safety assessments. Subjects will either return to the clinic/hospital, or, if possible and agreed by investigator and subject, have home visits conducted by certified healthcare professionals, for Visits 17, 19, and 20. The Observation Period begins the day after the final dose of IMP (ie, Visit 13, Day 43); Visit 15 (Day 50) is the first visit in the Observation Period.

Figure 2–1 presents a schematic diagram of the study design.

Figure 2–1: Schematic diagram

2.4 Determination of sample size

The primary efficacy endpoint of this study is change in QMG score from Baseline to Visit 9 (Day 29).

The sample size calculation use a 1-sided [redacted] significance level, an estimate (based on a [redacted] Confidence Interval [CI]) of the Standard Deviation (SD) for change in QMG of [redacted] and an anticipated treatment effect of [redacted] (Zinman et al, 2007).

Assuming a treatment difference of [redacted] points in the mean change from Baseline in QMG at Visit 9 between the placebo and UCB7665 treatment arm with SD equal to [redacted], a sample size of [redacted] subjects ([redacted] for each treatment group) provides >90% power to detect a treatment difference. Further it will be assumed that [redacted] of the randomized subjects cannot be utilized for the Full Analysis Set (FAS) and, hence [redacted] subjects will be randomized.

3 DATA ANALYSIS CONSIDERATIONS

3.1 General presentation of summaries and analyses

Statistical evaluation will be performed by PAREXEL. Analysis Data will adhere to CDISC (Clinical Data Interchange Standards Consortium) guidance documents for Analysis Data Model (ADaM) and follow their UCB interpretation.

All analyses will be performed using SAS version 9.3 or higher (SAS Institute, Cary, North Carolina, USA). Continuous variables will be summarized by visit (where applicable) including number of subjects (n), mean, SD, median, minimum and maximum. Geometric coefficient of

variation (geoCV), geometric mean (geoMean) and 95% CI for the geoMean will also be presented in the descriptive statistics for the PK and PD concentration data. Categorical variables will be summarized by visit (where applicable) with frequency counts and percentages.

When reporting relative frequencies or other percentage values, the following rules apply:

- For values where all subjects fulfill certain criteria, the percentage value will be displayed as 100
- For values where the absolute frequency is zero, there will be no percentage displayed at all
- All other percentage displays will use 1 decimal place

Percentages displayed based on continuous data (eg, percentage changes from baseline) will be displayed to 1 decimal place.

When reporting descriptive statistics, the following rules will apply in general:

- n will be an integer
- Mean (arithmetic and geometric), SD and median will use 1 decimal place more than the original data
- geoCV will be reported as a percentage to 1 decimal place
- Minimum and maximum will be reported using the same number of decimal places as the original value
- Correlations will use 3 decimal places
- If no subjects have data at a given time point, for example, then only n=0 will be presented. If n<3, then only n, minimum and maximum will be presented. If n=3, then only n, mean, median, minimum and maximum will be presented. The other descriptive statistics will be left blank.

Analyses will be performed by treatment group and for all subjects where stated. The treatment groups for Dosing Period 1 will be as follows and will be displayed as such in the TFLs:

- Placebo
- UCB7665 7mg/kg

For Dosing Period 2 and the Observation Period the following treatment groups will be considered for analysis and will be displayed as such in the TFLs (the first two groups will only be utilized for observation period, in case patients do not receive any dosing in period 2):

- Placebo
- UCB7665 7mg/kg
- Placebo - UCB7665 7mg/kg
- Placebo - UCB7665 4mg/kg
- UCB7665 7mg/kg - UCB7665 7mg/kg
- UCB7665 7mg/kg - UCB7665 4mg/kg

These treatment groups will be used for all safety and efficacy analyses.

Unless stated otherwise, all statistical tests will be 1-sided and conducted at 0.05 alpha levels. For Dosing Period 2, only descriptive analyses will be performed.

Data listings containing all documented data and all derived data will be generated.

3.2 General study level definitions

3.2.1 Analysis time points

3.2.1.1 Relative day

Relative day for an event will be derived with the date of the first sc infusion of study drug as reference.

Relative days for an event of measurement occurring before the date of first sc infusion are calculated as follows:

$$\text{Relative Day} = [(\text{Event Date} - \text{Date of First Infusion})]$$

The relative day for an event or measurement occurring on or after the reference date to the date of the last infusion is calculated as follows:

$$\text{Relative Day} = [(\text{Event Date} - \text{Date of First Infusion}) + 1]$$

For events or measurements occurring after the date of the last sc infusion, relative day will be prefixed with '+' in the data listings and will be calculated as follows:

$$\text{Relative Day} = + [(\text{Event Date} - \text{Date of Last Infusion})]$$

There is no relative Day 0. Relative day is not calculated for partial dates in cases where relative day is shown in a subject data listing. In such cases, relative day should be presented as '- -' in the subject data listings.

3.2.2 Study periods

The maximum duration of the study per subject will be approximately 18 weeks, consisting of the following 3 periods:

- Screening Period: 1 to 28 days
- Treatment Period: 6 weeks
 - Dosing Period 1 of 4 weeks. This period will start at the first actual dosing of Period 1.
 - Dosing Period 2 of 2 weeks. This period will start at the first actual dosing of Period 2.
- Observation Period: 8 weeks

The end of the study is defined as the date of the final clinic/hospital visit of the final subject in the study.

In the case a subject does not receive dosing in Dosing Period 2, the rule for entering the Observation Period given in [Section 2.3](#) will be generalized such that the subject will enter the Observation Period the day after the last dosing of Dosing Period 1. All data up to the missed dose will be treated according to plan, including data planned on the dosing day prior to the actual dosing.

The following definitions for starting and entering the study periods will be applied:

- Started period 1 is defined as all subjects in the safety set. Completed period 1 includes those subjects who have completed assessments prior to the first study treatment of Period 2 (Day 29).
- Started period 2 is defined as having received treatment on Period 2 Day 29. Completed period 2 includes those subjects who have completed assessments on Observation Period Day 50.
- Started Observation Period is defined as having assessments on Observation Period Day 50. Completed observation period includes those subjects who have a completed status in the study termination case report form

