8.5 Premature End of Treatment Visit

and any extensions or variations thereof. All subjects who withdraw early from the study treatment should aftend a PEOT Visit which will be scheduled as close as possible to the date of the decision for the study or treatment withdrawal. Subjects are encouraged to return to the clinic for all visits of the Observation Period following the PEOT Visit. An FV will be scheduled 8 weeks after the subject's final dose. In case a subject is not willing to attend the visits in the Observation Period, the subjects should still be strongly encouraged to attend at least the PEOT Visit and FV.

The assessments to be done at the PEOT Visit are the same as those at the FV (Visit 20).

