5 STUDY POPULATION CHARACTERISTICS

5.1 Subject disposition

The number of subjects who were enrolled, dosed, subjects included in each analysis set, and subjects who completed or prematurely discontinued the study/the period, as well as the reason

for discontinuation, discontinuation due to AEs, will be presented by dose arm and overall. Screen failure reasons will be summarized, based on the ES.

In addition the following listings will be presented by dose arm:

- Subject disposition (ES)
- Study discontinuation (ES)
- Visit dates (RS)
- Subject analysis sets (ES)

Subject disposition will be listed by treatment group based on the ES, and will include the date of informed consent, presence of informed consent for SFEMB with date, date of randomization for Dosing Period 1 and Dosing Period 2, date and time of first and last dose of IMP, date of premature termination and primary reason, and date of final contact.

The listing of study discontinuation will include the reason for discontinuation, period of discontinuation, with dose and number of days on that dose and the total number of days on study medication.

The number of days on IMP will be calculated as follows:

Number of days on IMP=[(Date of Last Dose Received)-(Date of First Dose Received)]+1

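### SAP 3.2.2 counts Period 2 completion and Observation Period entry by Day 50 assessments alone, so some subjects who stop study drug early are miscounted in the period-level disposition figures

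*SAP*

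**What the plan says.** SAP 3.2.2 (Study periods) sets the rules for starting and completing each period:

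- Period 2 start needs a dose: "Started period 2 is defined as having received treatment on Period 2 Day 29".
- Period 2 completion needs only a visit: "Completed period 2 includes those subjects who have completed assessments on Observation Period Day 50".
- Observation Period start rests on the same visit: "Started Observation Period is defined as having assessments on Observation Period Day 50".
- Observation Period completion is taken from the status on the study termination form.

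The same section has a separate entry rule for a subject who is not dosed in Period 2: "the subject will enter the Observation Period the day after the last dosing of Dosing Period 1". SAP 3.1, repeated in 3.6 and 11, keeps Placebo and UCB7665 7mg/kg groups for these subjects: "the first two groups will only be utilized for observation period, in case patients do not receive any dosing in period 2".

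SAP 5.1 tabulates by dose arm, among other counts, the subjects who "completed or prematurely discontinued the study/the period". Protocol 8.5 asks early stoppers to stay in follow-up: "Subjects are encouraged to return to the clinic for all visits of the Observation Period following the PEOT Visit". If they decline, it presses for at least the premature end of treatment (PEOT) visit and the final visit, the latter 8 weeks after the last dose.

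**The concern.** The protocol separates stopping study drug from leaving the study. Protocol 6.4 lists events that end dosing without ending participation, and 7.8.2 and 8.5 then encourage those subjects to attend the Observation Period visits, of which Day 50 (Visit 15) is the first. So a subject who stops drug partway through Period 2 and follows the protocol will usually have a Day 50 assessment, and the SAP rule then records that subject as having completed the period.

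The Observation Period has two start rules in one section. One places a Period 1 stopper in the period the day after the last dose. The other says the period has started only if Day 50 is assessed. The data columns created for these subjects follow the first rule and the disposition counts follow the second. A subject can therefore contribute Observation Period data without being counted as having started that period.

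At stake is whether a reader of the disposition table can tell how many subjects received the planned Period 2 infusions, and whether its Observation Period counts match the subjects summarised there.

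**Working it through.** The plan states no figure to reproduce. The check is to apply the SAP 3.2.2 rules to every possible stopping point.

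**Inputs.** Planned doses fall on Days 1, 8, 15 (Period 1) and 29, 36, 43 (Period 2), from the protocol schedule (Table 5.1). The final visit for an early stopper is the last dose + 56 days (Protocol 8.5).

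**Calendar check.** 43 + 7 = Day 50 (Visit 15). 43 + 56 = Day 99 (final visit). 4 + 6 + 8 = 18 weeks maximum. All agree with the documents.

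**Classification under the literal rules.**

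| Last dose | Doses received | Final visit due | Started Period 2 | Day 50 assessed: completed Period 2 / started Observation | Day 50 not assessed: completed Period 2 / started Observation |
|---|---|---|---|---|---|
| Day 1 | 1 | 1 + 56 = Day 57 | no | yes / yes | no / no |
| Day 8 | 2 | 8 + 56 = Day 64 | no | yes / yes | no / no |
| Day 15 | 3 | 15 + 56 = Day 71 | no | yes / yes | no / no |
| Day 29 | 4 | 29 + 56 = Day 85 | yes | yes / yes | no / no |
| Day 36 | 5 | 36 + 56 = Day 92 | yes | yes / yes | no / no |
| Day 43 | 6 | 43 + 56 = Day 99 | yes | yes / yes | no / no |

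**Reading the table.**

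1. Last dose Day 29 or 36, Day 50 assessed: a Period 2 completer with one or two of the three infusions.
2. Last dose Day 1, 8 or 15, Day 50 assessed: correctly counted as started Observation but, read literally, also a Period 2 completer who never started Period 2. If completion is meant to apply only within those who started, this disappears, but the SAP does not say so.
3. Last dose Day 1, 8 or 15, Day 50 not assessed (for example PEOT and final visit only): not counted as started Observation, although the entry rule puts the subject there on Day 2, 9 or 16.
4. Last dose Day 43, Day 50 missed: all six doses received, yet neither a Period 2 completer nor an Observation starter.

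**Scale.** About 42 subjects over four sequences is 42 / 4 = 10.5 each, so one misclassified subject moves a completion percentage by 1 / 10.5, or about 10 points. For illustration only, let s be the proportion of Period 2 starters who stop drug early and a the proportion of those who attend Day 50, with every fully dosed subject attending. Reported completion is (1 − s) + s·a, against a dosing completion of 1 − s.

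| s (assumed) | Dosing completion | Reported completion, a = 0.6 to 1.0 (assumed) |
|---|---|---|
| 0.1 | 0.90 | 0.96 to 1.00 |
| 0.2 | 0.80 | 0.92 to 1.00 |
| 0.3 | 0.70 | 0.88 to 1.00 |

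**The case against.** There are four serious points on the other side.

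- **Attendance is a coherent basis for completion.** SAP 3.2.2 also defines Period 1 completion by assessments done before the first Period 2 dose. This stands as a design choice. It does not explain why Period 2 completion is not tied to having started Period 2, nor does it remove the two Observation start rules.
- **Early stops are reported elsewhere.** SAP 11.2 summarises discontinuations due to adverse events by period and group, SAP 11.1 lists every infusion, and the SAP 5.1 disposition listing gives the date of the last dose. This largely stands. A reader might infer that the rule hides early drug stops; for adverse-event stops that is not supported. What remains is narrower. SAP 7 plans no specific compliance analysis, SAP 11.1 plans a listing and no count of infusions received, and stops for rescue or prohibited medication have no summary corresponding to the adverse-event one.
- **Period 1 stoppers are recognised.** A reader might infer that subjects who stop in Period 1 are, as a class, left out of the Observation Period. The documents do not support that. Day 50 falls before the final visit for all of them, those assessed at Day 50 are counted, the entry rule covers them and dedicated columns exist. Only those without a Day 50 assessment are missed.
- **Some cases depend on unstated detail.** The SAP does not say whether Day 50 means the calendar day or the Visit 15 label for a Period 1 stopper, or whether a PEOT assessment mapped to the next scheduled visit under SAP 3.2.3 counts. Nor is the termination form available, so whether a subject could complete an Observation Period not started is uncertain.

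**Conclusion.** The point holds in a limited form. As written, SAP 3.2.2 counts a subject who stops drug during Period 2 as a completer if Day 50 is assessed, allows a literal reading under which a subject completes Period 2 without starting it, and gives two conflicting start rules for the Observation Period. SAP 6.4.4 adds a third boundary when assigning medications: Day 50 or 7 days after the last dose.

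The effect is confined to the period-level disposition counts in SAP 5.1. The primary analysis at Visit 9, the Full Analysis Set and the Safety Set do not use these definitions. Adverse events have their own period assignment in SAP 11.2, and Period 2 is descriptive only.

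A reader might also take Period 2 completion as the trial's tolerability measure for 7mg/kg against 4mg/kg. No section gives it that role; the named safety variable is adverse events leading to withdrawal of study drug, which does not depend on SAP 3.2.2.

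The number of subjects affected is unknown. The stopping and attendance rates used above are assumptions, and the shift of about 10 points per subject follows from the small groups, so it would apply to any single misclassification.

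**What to change.** In SAP 3.2.2:

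1. Make completion of Period 2 conditional on having started it.
2. Adopt one Observation Period start rule, consistent with the entry rule already in that section, and apply it to both the counts and the summaries. State whether Day 50 means the calendar day or Visit 15, and whether a mapped PEOT assessment qualifies.

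In SAP 5.1, show completion of the three Period 2 infusions, or discontinuation of study drug, as a row separate from visit or study completion.

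Align the Observation Period boundary in SAP 6.4.4 or say why it differs.

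The cost is SAP wording and minor programming. Dosing dates, visit dates and termination status are already collected, so no new data or protocol change is needed.
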